Each pedicle screw trajectory will be independently queried using both triggered electromyography (EMG) and mechanomyography (MMG). In parallel to the EMG assessments, the threshold levels for each trajectory will be individually recorded using the SENTIO MMG ball tip probe, followed by querying of the tap, and finally of the pedicle screw itself. Threshold stimulation data will be recorded for each neuromonitoring device. No data about the EMG device itself will be collected. In case of a suspected thin wall or pedicle breach using either modality, particularly when a triggered EMG current threshold of 10 mA or less is noted, the surgeon will have the option of refashioning the trajectory based on ethical surgical judgment principles. However, the surgeon will need to re-record the new trajectory-specific triggered EMG and MMG threshold stimulation values.

After an acceptable trajectory has been determined and stimulation values recorded, the rest of the surgery will proceed with the standard of care procedures. Following screw placement, the central part of the spinal canal is decompressed by laminectomy in cases of stenosis-related neurogenic claudication. In cases of radicular leg pain related to foraminal stenosis, partial facetectomies will be performed as needed to decompress the associated nerve roots. Titanium rods are then positioned interconnecting the screws on each side. The posterolateral cortical bony surfaces are then fully decorticated and supplemented with graft material on both sides.

An intra-operative CT/3D reformatted study (using 2-mm slices) will be performed in all cases immediately after all the hardware installation is completed. The pedicle breach determination measurements (primary outcome) will be based on these intra-operative scans. As per standard-of-care considerations, the surgeon will once again have the option of revising a screw trajectory based on the imaging findings, but will once again be required to re-record the new trajectory-specific triggered EMG and MMG threshold stimulation values. Post-operative care, including X-rays will follow the standard of care for subjects who undergo fusion procedures.

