
Potential Risks & Benefits

Risks

- Describe any potential risks – including physical, psychological, social, legal, ability to re-identify subjects, or other risks. Assess the seriousness and likelihood of each risk.

- Which risks may affect a subject's willingness to participate in the study?
- Describe likely adverse effects of drugs, biologics, devices or procedures participants may encounter while in the study.
- Qualitative research - describe ethical issues that could arise while conducting research in the field and strategies you may use to handle those situations.
- Describe any steps to mitigate these risks.

Benefits

- Describe potential direct benefits to study participants – including diagnostic or therapeutic, physical, psychological or emotional, learning benefits. This cannot include incentives or payments.
- State if there are no direct benefits.
- Describe potential benefits to society and/or general knowledge to be gained.

Describe why potential benefits are reasonable in relation to potential risks. If applicable, justify why risks to vulnerable subjects are reasonable to potential benefits.

Per the attached device information for usage document potential adverse events associated with SENTIO MMG include nerve damage, burns, sepsis, heart failure, CNS effects such as seizure and pulmonary failure. Such events could be serious but are very unlikely, occurring in less than 1% of cases. Both of these devices are standard of care and these risks are associated with the surgical procedure and present regardless of study participation. These risks will be discussed with the patient during the surgical consenting process, and any condition or comorbidity (e.g. pacemakers) that would place the subject at a known increased risk has been included in the criteria for exclusion. The combination of two devices, which is a deviation from standard of care, equates to no quantifiable additional risks for subjects because the process involves sequentially placing an EMG and then a MMG probe on the already inserted pedicle screw to assess for respective electrical responses. The potential AEs are inherent risks for the FDA approved device, and not a result of the study procedures themselves. No clinical decisions will be made pertaining to the results of the monitoring systems utilized in the research setting.

A breach in confidentiality is unlikely, but possible and could lead to psychological distress.

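### Flagged trajectories that are refashioned before the only CT get no reference grade, so without a pairing rule the accuracy table can answer a different question from the stated objective

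*Combined protocol and SAP*

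**What the plan says.** The Objectives make comparative sensitivity and specificity for intraoperative detection of Grade C, D or E breaches the primary purpose. Study Design says that both devices assess all pedicle trajectories and that their readings are compared for accuracy.

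Research Procedures (Intra-Operative Procedures) sets this order of events:

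- Each trajectory is queried with both devices. MMG thresholds are recorded "using the SENTIO MMG ball tip probe, followed by querying of the tap, and finally of the pedicle screw itself".
- If there is "a suspected thin wall or pedicle breach using either modality, particularly when a triggered EMG current threshold of 10 mA or less is noted", then "the surgeon will have the option of refashioning the trajectory based on ethical surgical judgment principles". New EMG and MMG values must be recorded for the new trajectory.
- "After an acceptable trajectory has been determined and stimulation values recorded", the operation continues.
- One scan is described: "An intra-operative CT/3D reformatted study (using 2-mm slices) will be performed in all cases immediately after all the hardware installation is completed".
- The plan takes its primary grade from that scan: "The pedicle breach determination measurements (primary outcome) will be based on these intra-operative scans".
- After the CT the surgeon may revise a screw again, and "will once again be required to re-record the new trajectory-specific triggered EMG and MMG threshold stimulation values". No repeat CT is described.

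Potential Risks & Benefits states: "No clinical decisions will be made pertaining to the results of the monitoring systems utilized in the research setting". It also describes both probes as being placed on the screw once it is inserted, with no mention of probe-tip or tap readings.

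Data Collection & Research Materials lists threshold values for both devices. It does not say which reading is set against the CT grade, or what happens to readings from a trajectory that was replaced. No MMG cut-off is given. The EMG figure of 10 mA appears as a prompt for possible refashioning, not as a rule for calling a reading positive.

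**The concern.** A first-pass trajectory (the one made before any refashioning) that is flagged and then refashioned has EMG and MMG readings but is never graded. One that is flagged and left in place is graded, and so is one that is not flagged. Whether a reading is checked against the reference therefore depends on the tests under study. This is partial verification, in which positives are checked less often than negatives.

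The correct flags that the surgeon acts on are the ones lost. If the remaining table is reported as accuracy for detecting breaches, it answers a different question, and part of any difference between devices may reflect which flags were acted on. The missing pairing rule adds a second problem: setting first-pass readings against the CT of a replacement trajectory would push specificity the other way.

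**Working it through.** **Inputs.** The documents give no refashioning rate, no assumed sensitivity or specificity, and no per-screw rate of Grade C–E breach. The 1.35% in the background is a patient-level complication rate. The only figure used from the documents is 300 screws (Subject Demographics). Everything else is assumed: both devices have true sensitivity 0.80 and specificity 0.90, and 5%, 10% or 15% of first-pass trajectories are breached. Rates are written *a*/*m*: *a* is the share of EMG-positive trajectories refashioned, *m* the share of MMG-only positives.

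**Direction when all flags are acted on at one rate R.** Let F be the probability that a breached trajectory is flagged by either device. Observed sensitivity = Se × (1 − R)/(1 − R×F). As F ≤ 1, this cannot exceed Se. The same algebra shrinks the false-positive rate, so specificity cannot fall.

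**Cells**, ordered (both +, EMG only, MMG only, both −):

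- Independent: breached 0.64, 0.16, 0.16, 0.04; unbreached 0.01, 0.09, 0.09, 0.81.
- Correlated: breached 0.72, 0.08, 0.08, 0.12; unbreached 0.055, 0.045, 0.045, 0.855.
- Concordant: breached 0.80, 0, 0, 0.20; unbreached 0.10, 0, 0, 0.90.

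Keep (1 − *a*) of the first two cells, (1 − *m*) of the third and all of the fourth, then recompute. For independent 70%/30%, the breached cells become 0.192, 0.048, 0.112, 0.040 (sum 0.392). EMG sensitivity is 0.240/0.392 = 0.612 and MMG 0.304/0.392 = 0.776. The unbreached cells become 0.003, 0.027, 0.063, 0.81 (sum 0.903). Specificity is 1 − 0.030/0.903 = 0.967 and 1 − 0.066/0.903 = 0.927.

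| Agreement | *a*/*m* | Sens. EMG | Sens. MMG | Spec. EMG | Spec. MMG |
|---|---|---|---|---|---|
| Independent | 10%/10% | 0.796 | 0.796 | 0.908 | 0.908 |
| Correlated | 50%/30% | 0.694 | 0.722 | 0.947 | 0.937 |
| Correlated | 70%/30% | 0.577 | 0.654 | 0.967 | 0.948 |
| Independent | 70%/30% | 0.612 | 0.776 | 0.967 | 0.927 |
| Independent | 30%/90% | 0.909 | 0.753 | 0.921 | 0.982 |
| Concordant | 70%/30% | 0.545 | 0.545 | 0.968 | 0.968 |

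In the 30%/90% row EMG sensitivity rises above its true 0.80: 0.560/0.616. In the concordant row unequal rates create no gap. Equal rates do not guarantee an unbiased difference either: with true sensitivities 0.70 and 0.90, independent, 50% for both, the results are 0.350/0.515 = 0.680 and 0.450/0.515 = 0.874, so 0.20 becomes 0.194.

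**Adding replacement trajectories** (3% breached, assumed; independent 70%/30%; 10% breached at first pass). The refashioned share is 0.1 × 0.608 + 0.9 × 0.097 = 0.1481. Replacements add 0.0044 breached and 0.1437 unbreached. Sensitivity becomes 0.631 and 0.778; specificity 0.957 and 0.923.

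**Pairing first-pass readings with the replacement's CT** (same inputs). The refashioned share by cell is 0.7 × 0.073 = 0.0511, 0.7 × 0.097 = 0.0679 and 0.3 × 0.097 = 0.0291, and 97% of each is graded unbreached. EMG specificity = 1 − (0.0270 + 0.1154)/0.9564 = 0.851. MMG specificity = 1 − (0.0594 + 0.0778)/0.9564 = 0.857. Both fall below the true 0.90.

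**Bounds on the MMG − EMG sensitivity difference** (300 first-pass trajectories, all or none of the refashioned ones breached within each positive cell, none refashioned from the both-negative cell). For correlated 50%/30% at 10% breached, 17.28 breaches are verified and 29.9 trajectories are ungraded, of which 7.275 are EMG-only and 4.365 MMG-only.

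- Lower: (1.68 − 1.20 − 7.275)/(17.28 + 7.275) = −0.28.
- Upper: (1.68 + 4.365 − 1.20)/(17.28 + 4.365) = +0.22.

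At 5% and 15% breached the bounds are −0.43 to +0.35 and −0.20 to +0.17. At 10% breached they are −0.57 to +0.52 for independent 70%/30% and −0.10 to +0.10 for independent 10%/10%.

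**The case against.** The strongest reply is that the plan defines breach on the scanned screws. The primary outcome comes from a CT taken after installation, and each replacement trajectory must have its own readings. On that reading nothing is missing, and the table is correct for what was scanned. This stands for accepted trajectories. It does not settle the target, because the Objectives speak of intraoperative detection and Study Design of all pedicle trajectories.

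Second, the size may be small. The large gap needs both unequal rates and independent errors, although both devices test the same trajectory. Most of the figures above also omit replacement trajectories, which would enter the table and dilute the effect. In another assumed setting (5% breached; EMG 0.70/0.90, MMG 0.85/0.95; 90% of all flags refashioned), adding them moves EMG sensitivity from 0.50 to 0.61 and MMG from 0.61 to 0.74. If the statement in Potential Risks & Benefits governs, the refashioning rate is zero. All of this stands.

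Third, the detailed protocol and the case report forms were not supplied and may hold the rules.

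Two stronger readings are tempting. A reader might infer that EMG is penalised because the text singles out its 10 mA threshold. The documents do not support this: either device may prompt refashioning, no rates are given, and the 30%/90% and concordant cases show a reversed gap and no gap. A reader might also infer that the primary table certainly covers accepted trajectories only, or is invalid. The first is an inference from the procedure, since no pairing rule is written. The second is wrong for residual breaches.

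**Conclusion.** The concern holds in a limited form. Verification of first-pass readings depends on the tests being compared, and the supplied text has no rule for pairing readings with CT grades. Paired with the scanned trajectory's own readings, which is the natural reading of Research Procedures, the table is valid for residual breaches in accepted trajectories. As accuracy for breaches as first made, it tends to understate sensitivity and overstate specificity when both devices' flags are acted on at similar rates. When the rates differ, the comparison can be biased in either direction and one device's sensitivity can rise. Pairing first-pass readings with a replacement's CT would tend to make specificity too low.

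The size cannot be known from the documents. With assumed inputs and replacements omitted, it runs from almost none (equal 10%) to a sensitivity gap of 0.16 between identical devices (independent, 70%/30%). The two sections also contradict each other on whether readings may influence a trajectory. This should be fixed, and it becomes more serious as the observed refashioning rate rises.

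**What to change.** 1. Pair each CT grade with the EMG and MMG readings of the scanned trajectory taken before that CT, at one named stage (probe, tap or screw) used for both devices. Never pair superseded readings with a replacement's CT. Exclude readings re-recorded after a post-CT revision unless there is a new scan.
2. Label the result as accuracy for residual breaches in accepted trajectories, and do not present it as accuracy for detecting all breaches.
3. State the EMG and MMG cut-offs used to call a reading positive in the analysis. Where superseded same-stage readings were kept, report refashioned trajectories by EMG × MMG result, with all-or-none bounds on sensitivity, specificity and their differences. State that these bounds do not cover trajectories abandoned before that stage. Where readings were not kept, report the number missing as a limitation. Use Begg–Greenes weighting only as a sensitivity analysis, because it assumes that refashioning is unrelated to breach status within a cell. With independent tests and 10% breached, if 80% of breached and 40% of unbreached EMG-positives, and 40% and 20% of MMG-only positives, are refashioned, it returns 0.776 and 0.865 when both sensitivities are 0.80.
4. Reconcile Research Procedures with Potential Risks & Benefits on whether readings may alter a trajectory and on the stages at which readings are taken.

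If the detailed protocol already sets these rules, cite them instead.

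The cost is a little more analysis and wider, less favourable intervals; no patient or scan is added. Additional Information/Materials records enrollment and follow-up as complete, so nothing can be collected prospectively. Future Use and Sharing of Material lists device recordings among the retained data, but the documents do not say that superseded readings were kept. If they were not, item 3 reduces to the cut-offs and a stated limitation, and the other items still apply.

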- *Qualitative research:* Indicate ranges where flexibility is needed, if a fixed interview transcript is not available, describe interview topics including the most sensitive potential questions.
- *Research Repositories:* If the purpose of this submission is to establish a Research Repository (bank, registry) and the material you plan to collect is already available from a commercial supplier, clinical lab, or established IRB approved research repository, provide scientific justification for establishing an additional repository collecting duplicate material. Describe the repository design and operating procedures. For relevant information to include, see the [UK Research Biospecimen Bank Guidance](#) or the [UK Research Registry Guidance](#).

This study will be conducted solely at the University of Kentucky and is designed as a prospective post-market evaluation of the comparative sensitivity and specificity of mechanomyography versus triggered electromyography for the intraoperative assessment of pedicle breaches during instrumented lumbosacral (L1-S1) spine surgery. The 'control' triggered electromyography will be performed concurrently along with the 'experimental' mechanomyography assessments of all pedicle trajectories. Physiological readings from the

control EMG and the experimental MMG will be recorded and compared to see if one system is more accurate than the other. No data on or about the EMG neuromonitor will be collected as study data. CT-based assessment scales are generally regarded as the current optimal method to characterize the relative success of pedicle screw trajectories. In this study, pedicle screw trajectories will be assessed using the subjects' intra-operative CT/3D reformatted images. At the standard of care 6 week and 3 month follow-up time points, we will also assess for any improvements in pain and disability scores using completed questionnaires (NRS, ODI v2.1a, and PROMIS Global-10). All parts of the surgical procedure and assessments of pedicle screw placement using radiographic technology will be standard of care for the procedure being performed with the exception of the use of the two neuromonitoring systems that are being compared.

In this study, pedicle screw trajectories will be assessed separately by two study investigators using the subjects' intra-operative CT/3D reformatted images. Trajectory accuracies will be determined using a widely employed 2-mm increment grading system.

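### The risk section separates MMG adverse events from the study procedures on the strength of three statements that the same application contradicts, so MMG-related harm could be labelled unrelated

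*Combined protocol and SAP*

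**What the plan says.** Potential Risks & Benefits lists serious but rare events for the SENTIO MMG device, put at under 1% of cases, and then makes five linked statements:

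- On the source of the risk: "Both of these devices are standard of care and these risks are associated with the surgical procedure and present regardless of study participation".
- On using MMG together with EMG: "The combination of two devices, which is a deviation from standard of care, equates to no quantifiable additional risks for subjects".
- The reason given for that: "because the process involves sequentially placing an EMG and then a MMG probe on the already inserted pedicle screw".
- On attribution: "The potential AEs are inherent risks for the FDA approved device, and not a result of the study procedures themselves".
- On consequences for care: "No clinical decisions will be made pertaining to the results of the monitoring systems utilized in the research setting".

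Data and Safety Monitoring makes an event reportable when three conditions hold together: it is serious, it is unexpected, and it is related to the study procedure. The available text does not define relatedness. A detailed protocol is listed as an attachment under Additional Information/Materials, but it is not part of the text and may contain a definition.

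**The concern.** SENTIO MMG is the device named as under test in Study Device Information. An adverse event of that device, or of an action taken because of its reading, is what a relatedness judgement in this study has to address. The risk section is the only available text that says how such events should be attributed, and it points away from the study.

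If its supporting statements are wrong, two things follow. The added risk of taking part is misdescribed, in a study that anticipates no direct benefit to subjects. And anyone judging relatedness by the risk section could label MMG-related harm as unrelated. For harm after an MMG-prompted change of trajectory the section offers no attribution at all, because it denies that such a decision is made.

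**Working it through.** No arithmetic applies: the plan states no figure for this point, so the check sets each statement beside the rest of the application.

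**1. Risk present regardless of participation.** Available Alternative Opportunities/Treatments says that a patient who declines has the usual surgery without MMG. The Informed Consent Process identifies MMG and its comparison with EMG as the only investigational part of the operation. A risk specific to MMG cannot be present in a patient who does not receive MMG. The statement fails for MMG-specific risk. It may hold for EMG and for the surgery itself.

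**2. Contact only with a screw already in place.** Intra-Operative Procedures says MMG thresholds are recorded for each trajectory "using the SENTIO MMG ball tip probe, followed by querying of the tap, and finally of the pedicle screw itself". Two of the three stages precede the screw, and new values must be recorded after any refashioning. The statement fails. It is also the only one of the three explicitly offered as the reason for no added risk.

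**3. No clinical decisions.** The same section gives the trigger for redoing a trajectory: "In case of a suspected thin wall or pedicle breach using either modality". It mentions an EMG threshold of 10 mA or less as a particular case, which adds emphasis but does not exclude MMG. The qualifier about the research setting does not rescue the statement, because MMG is used here only as research. The statement fails.

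**4. From statements to labels.** Three kinds of event can be traced through the reporting rule:

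- *An event on the device list, caused by MMG.* The risk section points to unrelated. Because it is listed, it is expected and would generally not be reportable whatever its relatedness. Only the label changes.
- *An unlisted event caused by MMG contact.* The attribution sentence concerns the potential events just listed, so it does not literally exclude this one. The outcome depends on a relatedness definition that the text does not give.
- *Harm from an MMG-prompted refashioning.* The risk section says no such decision occurs, so it gives no attribution. The outcome again depends on the missing definition.

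**5. Whether relatedness has been used.** It has. The Continuation Review lists four adverse events from the preceding 12 months, including an intra-operative CSF leak, and records the investigator's judgement that none is related to the study. It does not say whether MMG interrogation or refashioning counted as a study procedure in that judgement.

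**The case against.** The strongest reply is that little turns on this. Much of it stands.

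- *Reporting.* The three conditions apply jointly, and listed device events mostly fail the unexpected condition anyway. A reader might infer that the risk section takes MMG harm out of reporting. The documents do not support that: few events would become reportable through relatedness alone.
- *Capture.* All intra-operative and peri-operative complications go on the case report forms whatever their relatedness, and device-related events are a named category at follow-up. The four events in the Continuation Review reached the IRB although judged unrelated. An inference that events are being lost is not supported.
- *Misclassification.* A reader might take the CSF leak as an example of a wrong label. Nothing in the text shows that it, or any other event, was wrongly classified.
- *Self-contradiction over standard of care.* It is tempting to say the risk section contradicts itself by calling both devices standard and their combination a deviation, and to add the Study Design wording that all is standard "with the exception of the use of the two neuromonitoring systems that are being compared". Both can be read as concerning dual use only, so they are not counted here. The first contradiction rests on the alternatives and consent sections.
- *Counting probe contacts.* The number of MMG readings taken before the screw is in does not measure harm. Nothing in the documents says those contacts are riskier, so no magnitude is drawn from them.
- *Timing.* Enrollment and follow-up are complete, so a correction protects no further subject. It still affects how recorded events are described.

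None of these replies restores any of the three statements.

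**Conclusion.** All three supporting statements are wrong as written, so the conclusion that device events do not result from the study procedures is unsupported. Following it could lead harm from MMG, or from a refashioning that MMG prompted, to be labelled unrelated to the study.

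The consequence is limited to the risk description and the relatedness labels. The comparison of sensitivity and specificity is not affected. The effect on the number of related events cannot be sized, because the documents give neither the number of MMG-prompted refashionings nor a cumulative event list.

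The verdict rests on two assumptions: that the attached detailed protocol does not already define relatedness in a way that settles the matter, and that MMG was given only to participants, as the alternatives section implies.

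**What to change.** 1. Correct the three statements. MMG-specific risk arises from taking part; MMG is applied by ball tip probe, tap and screw, with repeats after refashioning; and a reading from either modality may lead the surgeon to redo a trajectory.
2. State that MMG interrogation at any stage, and any refashioning prompted by an MMG reading, counts as a study procedure when relatedness is judged. If the detailed protocol already says so, cite it.
3. Re-check the relatedness of all recorded complications and adverse events on that basis, using operative notes and case report forms.
4. Do not treat repeat values with a first EMG reading above 10 mA as evidence of an MMG prompt. Revisions made after the intra-operative CT also require re-recording, and EMG-prompted changes above 10 mA are possible. Such a screen would also miss MMG-prompted changes where EMG was at or below 10 mA. Where the reason for a refashioning was not recorded, say so.

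The cost is a wording correction and a short review of existing records, with no new data from subjects. The count of related events may rise slightly. The listed intra-operative data items include thresholds but none for a refashioning or its prompt, so some reasons may not be recoverable. The case report forms themselves are not in the text.
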